We are still following some participants in Study #6457 (which compared desvenlafaxine to placebo) and #6263 (AKA #7160R) (which compared sertraline to placebo, non-responders crossed to bupropion or sertraline, respectively). While unlikely, should any such patients be eligible for this study, we would approach them. We would not endeavor to make them eligible, for example, by stopping current treatment in order to produce eligibility.

Inclusion/Exclusion Criteria

Name the subject group/sub sample
nonbipolar depression

Create or insert table to describe the inclusion criteria and methods to ascertain them

- | | |
|---------------------------------------|---|
| 1. Age 18-65 | 1. Ask patient and compare stated age to reported DOB |
| 2. Currently depressed | 2. Has an affective disorder diagnosis per SCID interview (i.e., major depression, persistent depressive disorder, unspecified depressive disorder) |
| 3. In reasonably good physical health | 3. No active medical problem not under good control (e.g., someone with hypertension whose current blood pressure is in the normal range, someone with diabetes having a hemoglobin A1C < 7; abnormal thyroid tests [low TSH in someone taking thyroid medication is OK]; so, medical history (from patient), labs, and when indicated discussion with primary care physician |

Create or insert table to describe the exclusion criteria and methods to ascertain them

- | | |
|--|-------------------|
| 1. Bipolar disorder (I, II or unspecified) | 1. SCID interview |
|--|-------------------|

2. History of psychosis	2. SCID interview
3. Unstable medical condition	3. medical history, labs, physical examination
4. Current (past six months) drug or alcohol use disorder	4. SCID interview; urine toxicology
5. Need for hospitalization	5. Clinician's judgment based on depression severity, suicidality or any other reason
6. Treating clinician determination not to include patient in this protocol	6. Clinician's judgment
7. Currently taking medication approved for the treatment of depression	7. Patient report
8. Un- or poorly controlled hypertension	8. BP on repeated readings of ≥ 150 systolic or ≥ 100 diastolic
9. Pregnancy	9. Patient report; lab test

Waiver of Consent/Authorization

Indicate if you are requesting any of the following consent waivers
 Waiver of consent for use of records that include protected health information (a HIPAA waiver of Authorization)
 No
 Waiver or alteration of consent
 No

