Ratings and timing of ratings will be identical for all patients. That is, all will complete the same rating scales throughout. In particular, all subjects will log in for 12 hours out of 24 during their initial 24 hours post-randomization, complete daily mood, sleep and energy logs, wear an activity monitor and have call-in interviews daily during the first post-randomization week. All will be interviewed by an independent evaluator blind to treatment assignment at baseline and Weeks 1 and 6, with ratings by their study clinician daily for the first week and weekly thereafter. At week 6, remitters will be recommended to continue bright light and allowed sleep times, although they will be asked to return their light boxes, goggles and activity monitors. Nonremitters will be offered alternative treatment, including Chronotherapy if assigned to the alternative treatment group and standard antidepressants whichever their assigned study treatment. All randomized subjects will continue to be seen at least monthly for six months with continued ratings each month.

Use of Light Boxes

All fecund women will be instructed to stop using the light box should they become pregnant. Also, regardless of group assignment, patients will be instructed to sit about 18 inches from the light box with eyes open but not looking directly at the light; instead they should read or use their computer or other sedentary activity. They should remain 18 inches from the light for 30 minutes. However, should side effects occur (e.g., overstimulation), the time may be decreased. Tolerance of the light box plus continuing depressed mood will trigger the doctor recommending longer light box use in weekly 15 minute increments up to 60 minutes total; first available increment would be at the week 2 visit, decrements can occur at any time.

Melatonin

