3. eye damage - while this has been listed as a risk, to our knowledge it has never been demonstrated. Indeed, the only prospective study of which we are aware (Gallin et al, 1995) found no eye/retinal changes after six weeks (N=50) or after 3-6 years (N=17). Indeed, sunlight is quite safe except for ultraviolet (UV) exposure and prolonged exposure to direct bright light; the light boxes we will use in this study do not emit significant UV light, nor is the 10,000 lux intensity of the light boxes we will use anywhere near the intensity of light known to produce retinal damage. To our knowledge, no ophthalmologist recommends that we avoid going outdoors between 9 a.m. and 4 p.m. when outdoor light is at or greater than 10,000 lux. See "Uploads" for the Gallin reference.

4. patient's depression may not improve - this, of course, is the risk of any treatment one might choose, or of not being treated. It is unclear, however, whether chronotherapy improves on not being treated or approximates/surpasses accepted treatments.

5. pregnancy - while it makes sense that simulated sunlight ought not to adversely affect a pregnancy, to our knowledge, this has not been studied so the affect of the bright lights we have patients use in this study must be considered of unknown risk to a pregnancy. We are also unaware of documentation of missed sleep or regulated sleep adversely affecting pregnancy, so also consider these to have unknown risk to pregnancy.

Describe procedures for minimizing risks

1. overstimulation - we have not seen overstimulation during Wake Nights, but have occasionally had patients report it at the end of a session using bright lights. Should it be reported during a Wake Night, the patient would be instructed to find a quiet dark place in which to sit or lie quietly, try to calm down and not worry should they fall asleep. In the more likely case that it occurs during or following light treatment, the patient would be instructed to decrease their light exposure by sitting further away from the lamp or sitting in front of the lamp for a shorter time. In the case of patients who experience overstimulation toward the end of their light exposure, they would be instructed to sit in front of the lights for the amount of time prior to their experience of overstimulation. Thus, if overstimulation began after 25 minutes, they would be instructed next time to sit in front of the lights for 20 minutes.

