2. fatigue - reassurance that fatigue will decrease as they recover their sleep in nights subsequent to their Wake Night. Should uncharacteristic (i.e., not present prior to treatment) fatigue continue after apparent sleep recovery, this will be take as evidence that the new timing of their sleep is out of sync with their biological clock such that a significant portion of their assigned sleep time is occurring when their biological clock insists they ought to be awake. That is, the paradigm has not shifted their clock. This will trigger a new attempt to shift their clock as is outlined for patients whose MEQ-determined ideal sleep time is more than two hours different from their desired sleep time. All patients will be warned re driving and using heavy/dangerous equipment during and following missed sleep as well as if significant fatigue occurs at other times.

3. eye damage - as damage from light is mainly attributed to exposure to ultraviolet rays and very high intensity light, this risk will be minimized by limiting bright light use to devices certified to emit only visible light; that is, not to emit UV light. And at a much lower intensity than used, for example in laser surgery or emitted by the noonday sun (> 100,000 lux, or more than 100 times the intensity of the emission of the light boxes we use [lux is measured on a logarithmic scale, not a linear scale]) which would damage the retina if stared at for too long a time. That is, the intensity of light used in this study is one the eye often experiences and one no one is warned against.

4. depression may not improve - as noted, this is a risk whether one pursues accepted treatment or does nothing. The odds of either treatment approach relieving a patient's depression is unknown and the purpose of this protocol is to begin determining those odds. Attention, a listening (hopefully) ear, activating oneself to come to weekly meetings may be expected to produce more benefit than not being engaged in treatment. While the protocol will not automatically remove patients whose symptoms do not improve prior to six weeks post-randomization, patients and clinicians will always have the option of discontinuing the protocol

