significant abnormality, and to evaluate retest results after an initial short-term treatment phase and after several years of treatment.

PATIENTS AND METHODS

RESEARCH VOLUNTEERS WERE SCREENED FOR PROSPECTIVE study according to National Institute of Mental Health diagnostic criteria for seasonal affective disorder⁴ and the Diagnostic and Statistical Manual of Mental Disorders, third edition, revised (DSM-III-R)¹⁵ (major depressive disorder, recurrent [296.3] or bipolar disorder not otherwise specified [296.7], both with seasonal pattern [winter type]). Patients entered clinical trials of light therapy between 1987 and 1991, after providing informed consent. Exclusion criteria included the following: (a) current treatment with psychotropic or photosensitizing medication, recent history of suicide attempt, panic or eating disorder unrelated to depression, or other DSM-III-R axis I disorder; (b) current use of alcohol, marijuana, cocaine, or stimulant drugs, including diet pills; (c) ocular abnormality including corneal or retinal pathology, cataract, or narrow-angle or primary open-angle glaucoma; and (d) nonocular conditions including skin cancer, head injury, epilepsy, diabetes, or diseases requiring treatment with beta-adrenergic blockers. At the time of entry into the study, all patients met clinical severity criteria¹⁶ for moderate to severe depression.

Before acceptance into the program, patients underwent a standard physical examination supplemented by electrocardiogram, urinalysis, and blood tests (complete blood cell count, including platelets, thyroid panel, cholesterol [high density lipoprotein, cholesterol/high-density lipoprotein ratio and triglycerides]), to rule out potentially complicating medical conditions.

Of 64 patients recruited into the study, two were excluded because of ophthalmologic indications. Because of scheduling constraints, five patients received only pretreatment ocular examinations and six received only posttreatment examinations (all with normal results). One patient refused a second examination with pupil dilation. To determine potential

short-term treatment effects, we analyzed the ocular results for the 50 patients who received both pretreatment and posttreatment ocular examinations during the year of entry into the study. This group included 13 men and 37 women, ages 18 to 62 years (mean \pm S.D., 39.28 \pm 11.38 years).

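### The written criteria contain no exclusion for known progressive retinal disease, which the protocol's own eye-safety source would still exclude; two eye-risk statements also need correcting.

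*Protocol*

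**What the plan says.** **Risk text.** Under Risks/Discomforts/Inconveniences (item 3, eye damage), the Protocol gives the light boxes as 10,000 lux. It relies on the one prospective study it knows of, which it says "found no eye/retinal changes after six weeks (N=50) or after 3-6 years (N=17"). Under the procedures for minimizing risks (item 3) it says "this risk will be minimized by limiting bright light use to devices certified to emit only visible light". It then compares the boxes with a noonday sun above 100,000 lux, which it describes as "more than 100 times the intensity of the emission of the light boxes we use", adding that lux is a logarithmic scale.

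**Eligibility.** The Inclusion/Exclusion Criteria require reasonably good physical health, defined as "No active medical problem not under good control". One example given of good control is "someone with diabetes having a hemoglobin A1C < 7". The exclusions include unstable medical condition and the treating clinician's decision not to include the patient. Neither table names an eye or retinal condition.

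**The uploaded eye study.** Its exclusions, listed under Patients and Methods, include "ocular abnormality including corneal or retinal pathology, cataract, or narrow-angle or primary open-angle glaucoma" and "nonocular conditions including skin cancer, head injury, epilepsy, diabetes".

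**The concern.** The Protocol's eye-safety argument rests on a null result from a study that kept patients with retinal pathology and diabetes out. This trial does not state the same restriction. A candidate with known diabetic retinopathy or macular degeneration could be randomised to daily bright light through clear goggles, on evidence that was not gathered in such patients.

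During the randomised six weeks this mainly concerns the Chronotherapy arm. The comparator wears amber goggles at the light box, although its non-remitters may be offered Chronotherapy afterwards.

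What is at stake is the safety of a small number of participants and the accuracy of the risk text that the review board reads. The efficacy comparison is not at stake.

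**Working it through.** **1. Eligibility set beside the source**

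| Point | Eye study | This trial |
|---|---|---|
| Retinal pathology | Excluded (Patients and Methods) | Not named |
| Diabetes | Excluded (Patients and Methods) | Acceptable if well controlled; retinopathy not mentioned |
| Would light worsen pre-existing eye disease? | Authors cannot say (Discussion) | Not discussed |
| Diabetic retinopathy, macular degeneration, retinitis pigmentosa | Would still be excluded (Discussion) | Not named |
| Exception for those diseases | Ophthalmologic monitoring, after medication has failed or not been tolerated (Discussion) | No ophthalmologic monitoring in the procedures or flow chart |
| Definite ocular contraindication | None can be specified (abstract) | None stated |

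The null result therefore does not reach patients with progressive retinal disease, and this trial lacks the monitoring on which the source's exception depends.

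**2. The stated margin**

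Inputs: noonday sun above 100,000 lux (procedures for minimizing risks, item 3); light box 10,000 lux (Risks, item 3). The stated ratio is more than 100.

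- Direct ratio: 100,000 / 10,000 = 10, so the margin is more than 10 times.
- Logarithmic reading: log10(100,000) − log10(10,000) = 5 − 4 = 1 unit, which is still a tenfold ratio.
- A hundredfold margin would need a sun of 100 × 10,000 = 1,000,000 lux, or a box of 100,000 / 100 = 1,000 lux.

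The stated figure cannot be reproduced from the Protocol's own inputs. The eye study's Discussion also treats lux as linear. It equates the dose of 10,000 lux for 30 minutes with that of 2,500 lux for two hours: 10,000 × 0.5 = 5,000 lux-hours and 2,500 × 2 = 5,000 lux-hours.

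**3. The stated short-term follow-up**

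The Protocol says six weeks for the 50 patients. The study's abstract gives two to eight weeks. Its methods say that the post-treatment examination came after about two weeks of light, with scheduling delays of up to two months in some cases. Six weeks lies inside the range but is not the follow-up the study reports.

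**The case against.** **Existing screens may be enough.** Medical history, labs, physical examination and, when indicated, a discussion with the primary care physician are already specified, and a known retinal disease is the kind of thing a history brings out. The good-control rule, the unstable-condition exclusion or the clinician's veto could then apply. This stands in part, and it is why the point is limited to what the written criteria allow. A reader might infer that the diabetes example admits patients with retinopathy. It does not say so: it illustrates good control and is not a rule admitting every patient with diabetes below that A1C.

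**The source is more permissive than its exclusions suggest.** Its remark about progressive retinal disease comes in a paragraph proposing that exclusions be narrowed. Its 50 patients included one with peripheral retinal degeneration and two with old chorioretinal scars, and none showed pathologic change attributable to light. This stands. A reader might infer that bright light is known to harm diseased retinas. The documents do not support that; the source leaves the question open.

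**Eye screening came before the review board.** The board's memorandum shows that members questioned whether an eye examination was needed, given the likely low risk. It also said that removing the examination would require re-review with a summary of eye risks. So the topic was not overlooked, but the memorandum does not address whether patients with known retinal disease should be excluded.

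**The wording errors change little.** This stands. The low-ultraviolet device and the intensity below noonday sun survive at a tenfold margin. A reader might infer from the follow-up error that this trial's light exposure goes beyond the evidence. It does not. Sessions start at 30 minutes and may rise in "weekly 15 minute increments up to 60 minutes total" from the week 2 visit, so the six-week maximum is 14 × 0.5 + 7 × 0.75 + 21 × 1.0 = 33.25 hours. The 17 long-term patients had at least 60 hours by the abstract; the lowest exposure figure in the results is 49.1 hours.

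**Conclusion.** The point holds as a minor improvement to participant safety. The written criteria do not name a group that the Protocol's own eye-safety source would continue to exclude, and the trial has no ophthalmologic monitoring to support that source's exception.

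The number affected is assumed to be very small at ages 18 to 65; the documents give no figure. Confidence is moderate because the screening protocol (#6669R) is not among the documents and the consent pages were removed, so eye questions or warnings may exist there.

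The wording errors are certain but confined to background risk text. The margin is overstated tenfold (more than 100 times against more than 10), the logarithmic remark is wrong, and six weeks is given where the source reports about two weeks, range two to eight. They alter no procedure, endpoint or analysis, and the SAP is unaffected.

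**What to change.** - **Inclusion/Exclusion Criteria:** add one exclusion row, *known progressive retinal disease (e.g., diabetic retinopathy, macular degeneration, retinitis pigmentosa)*, with the existing medical history as the method of ascertainment.
- **Procedures for minimizing risks, item 3:** change the margin to *more than 10 times* and delete the remark about a logarithmic scale.
- **Risks, item 3:** replace six weeks with *about two weeks (range two to eight)* for the 50 patients.

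The cost is one table row and two small text edits. No new examination or visit is needed. The only downside is the loss of a few candidates, assumed to be very few. The wording edits change nothing the trial does.

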- m-CGI		X	X	X	X	X	X	X	X											
- MMSE*	X																			
Independent Evaluator																				
- SIGH-ADS		X							X					X						
- CGI		X							X					X						
- IE Treatment Guess		X							X					X						
Patient-Rated Measures																				
- QIDS	X	X							X	X	X	X	X	X	X	X	X	X	X	X
- Expectation Form	X																			
- PGI	X	X							X	X	X	X	X	X	X	X	X	X	X	X
- MEQ	X	X												X						X
- SCL-90	X	X							X					X			X			X
- sleep log	X	X	X	X	X	X	X	X	X	X	X	X	X	X	X	X	X	X	X	X
- m-QIDS		X	X	X	X	X	X	X	X											
- m-PGI		X	X	X	X	X	X	X	X											
Laboratory and other																				

- PE	X																		
- labs	X																		
- saliva for melatonin		X						X											
- urine for pregnancy**	X						X												

* used only for those aged 60 and above

** **only for fecund women not already known to be pregnant**

KEY TO ABBREVIATIONS

CGI (Clinical Global Impression) - this is a clinician rated global measure of the patient's over-all psychopathology and improvement over the past week, improvement compared to pre-treatment

HIGH-C (Hypomania Interview Guide including Hyperthymia, Current Assessment Version) - this is a clinician-rated measure of manic/hypomanic symptoms rated over the past week

labs (laboratory examinations) - these include **EKG**, blood and urine; blood is examined for hematology (e.g., whether the patient is anemic) and routine blood chemistry (e.g., whether the patient has problems with their liver, kidney or thyroid); analysis of the urine determines whether there is a kidney

m-CGI - this is identical to the CGI except it measures the past 24 hours

m-HIGH-C - this is identical to the HIGH-C except modified to measure the past 24 hours

m-PGI - this is identical to the PGI except it is rated for the past 24 hours

m-QIDS - this is identical to the QIDS except it omits sleep and weight items and is rated for the past 24 hours

m-SIGH-ADS - this is identical to the SIGH-ADS except sleep and weight items are removed and ratings are for the past 24 hours

MEQ (Morningness-Eveningness Questionnaire) - this is a 19-item patient-rated questionnaire asking the times of the day respondents prefer to eat, sleep and perform various functions, like exercise, test-taking and working; answers indicate the timing of the individual's biological clock

MMSE (Mini-Mental Status Examination) – this is a standard method for evaluating whether someone is cognitively intact or demented

PE - physical examination

PGI (Patient Global Impression)- this is identical to the CGI except patient-rated, asking patients to rate their over-all symptoms over the past week and improvement relative to pre-treatment

QIDS-SR (Quick Inventory of Depressive Symptoms, Self-Rated) - this is a patient-rated 16-item measure of depressive symptoms which has been shown to correlate highly with the clinician-rated 30-item Inventory of Depressive Symptoms

SCID (Structured Clinical Interview for DSM Diagnoses) - this is a standard semi-structured interview enabling assignment of the major clinical diagnoses according to the DSM diagnostic system, both current and life-time

SCL-90 (90 item Symptom Check List) - this instrument includes 90 common psychiatric symptoms covering 9 areas of psychopathology, including depression, anxiety, psychosis

SIGH-ADS (Structured Interview Guide for the Hamilton Depression Rating Scale with Atypical Supplement) - this is a clinician-rated measure of depressive symptoms which generates scores for the 17, 21 and 25 item Hamilton Rating Scale for Depression as well as a score summarizing the 8 items intended to measure symptoms of atypical depression

Sleep Log - The patient completes this daily, 7 days to a page, indicating when sleep occurred, mood and energy each day, timing of light exposure and any medications

Independent Evaluator Treatment Guess

IE Name: _____

Patient Study ID _____

Date _____

Do you think the subject is currently being treated?

____ Yes

____ No

What treatment has this patient been receiving? (Even if you have no idea, please make a wild guess; if you think treatment has not begun, this answer would be "none")

How long has the patient been receiving this treatment? (If you think treatment has not begun, the answer would be "0")

_____ Days Weeks Months Years (insert # and circle the time period)

Why did you guess the patient was not being treated, or, if treated, what that treatment might be?

MORNINGNESS-EVENINGNESS QUESTIONNAIRE (revised)¹

Name: _____ Date: _____

For each question, please select the answer that best describes you by checking the corresponding box. Make your judgments based on how you have felt in recent weeks.

1. *Approximately* what time would you get up if you were entirely free to plan your day?

- 5:00 a.m. – 6:30 a.m.
- 6:30 a.m. – 7:45 a.m.
- 7:45 a.m. – 9:45 a.m.
- 9:45 a.m. – 11:00 a.m.
- 11:00 a.m. – 12 noon

Leave
this
section
blank:

5
4
3
2
1

2. *Approximately* what time would you go to bed if you were entirely free to plan your evening?

- 8:00 p.m. – 9:00 p.m.
- 9:00 p.m. – 10:15 p.m.
- 10:15 p.m. – 12:30 a.m.
- 12:30 a.m. – 1:45 a.m.
- 1:45 a.m. – 3:00 a.m.

5
4
3
2
1

3. If you usually have to get up at a specific time in the morning, how much do you depend on an alarm clock?

- Not at all
- Slightly
- Somewhat
- Very much

4
3
2
1

¹Some stem questions and item choices have been rephrased from the original instrument (Horne and Östberg, 1976) to conform with spoken American English. Discrete item choices have been substituted for continuous graphic scales. Prepared by Terman M, Rifkin JB, Jacobs J, and White TM. New York State Psychiatric Institute, [name]. Supported by NIH Grant MH42931. *See also:* automated version (AutoMEQ) at www.cet.org.

MORNINGNESS-EVENINGNESS QUESTIONNAIRE

Page 2

Leave
this
section
blank:

4. How easy do you find it to get up in the morning (when you are not awakened unexpectedly)?

- Very difficult 1
- Somewhat difficult 2
- Fairly easy 3
- Very easy 4

5. How alert do you feel during the first half hour after you wake up in the morning?

- Not at all alert 1
- Slightly alert 2
- Fairly alert 3
- Very alert 4

6. How hungry do you feel during the first half hour after you wake up?

- Not at all hungry 1
- Slightly hungry 2
- Fairly hungry 3
- Very hungry 4

7. During the first half hour after you wake up in the morning, how do you feel?

- Very tired 1
- Fairly tired 2
- Fairly refreshed 3
- Very refreshed 4

8. If you had no commitments the next day, what time would you go to bed compared to your usual bedtime?

- Seldom or never later 4
- Less that 1 hour later 3
- 1-2 hours later 2
- More than 2 hours later 1

MORNINGNESS-EVENINGNESS QUESTIONNAIRE

Page 3

- | | |
|--|------------------------------------|
| 9. You have decided to do physical exercise. A friend suggests that you do this for one hour twice a week, and the best time for him is between 7-8 a.m. Bearing in mind nothing but your own internal “clock,” how do you think you would perform? | Leave
this
section
blank: |
|  Would be in good form | 4 |
|  Would be in reasonable form | 3 |
|  Would find it difficult | 2 |
|  Would find it very difficult | 1 |
| | |
| 10. At approximately what time in the evening do you feel tired, and, as a result, in need of sleep? | |
|  8:00 p.m. – 9:00 p.m. | 5 |
|  9:00 p.m. – 10:15 p.m. | 4 |
|  10:15 p.m. – 12:45 a.m. | 3 |
|  12:45 a.m. – 2:00 a.m. | 2 |
|  2:00 a.m. – 3:00 a.m. | 1 |
| | |
| 11. You want to be at your peak performance for a test that you know is going to be mentally exhausting and will last two hours. You are entirely free to plan your day. Considering only your “internal clock,” which one of the four testing times would you choose? | |
|  8 a.m. – 10 a.m. | 6 |
|  11 a.m. – 1 p.m. | 4 |
|  3 p.m. – 5 p.m. | 2 |
|  7p.m. – 9 p.m. | 0 |
| | |
| 12. If you got into bed at 11 p.m., how tired would you be? | |
|  Not at all tired | 0 |
|  A little tired | 2 |
|  Fairly tired | 3 |
|  Very tired | 5 |

MORNINGNESS-EVENINGNESS QUESTIONNAIRE

Page 4

- | | |
|--|------------------------------------|
| 13. For some reason you have gone to bed several hours later than usual, but there is no need to get up at any particular time the next morning. Which one of the following are you most likely to do? | Leave
this
section
blank: |
|  Will wake up at usual time, but will not fall back asleep | 4 |
|  Will wake up at usual time and will doze thereafter | 3 |
|  Will wake up at usual time, but will fall asleep again | 2 |
|  Will not wake up until later than usual | 1 |
| 14. One night you have to remain awake between 4-6 a.m. in order to carry out a night watch. You have no time commitments the next day. Which one of the alternatives would suit you best? | |
|  Would not go to bed until the watch is over | 1 |
|  Would take a nap before and sleep after | 2 |
|  Would take a good sleep before and nap after | 3 |
|  Would sleep only before the watch | 4 |
| 15. You have two hours of hard physical work. You are entirely free to plan your day. Considering only your internal "clock," which of the following times would you choose? | |
|  8 a.m. – 10 a.m. | 4 |
|  11 a.m. – 1 p.m. | 3 |
|  3 p.m. – 5 p.m. | 2 |
|  7p.m. – 9 p.m. | 1 |
| 16. You have decided to do physical exercise. A friend suggests that you do this for one hour twice a week. The best time for her is between 10-11 p.m. Bearing in mind only your internal "clock," how well do you think you would perform? | |
|  Would be in good form | 1 |
|  Would be in reasonable form | 2 |
|  Would find it difficult | 3 |
|  Would find it very difficult | 4 |

MORNINGNESS-EVENINGNESS QUESTIONNAIRE

17. Suppose you can choose your own work hours. Assume that you work a five-hour day (including breaks), your job is interesting, and you are paid based on your performance. At *approximately* what time would you choose to begin?

Leave
this
section
blank:

- 5 hours starting between 4:00 – 8:00 a.m. 5
- 5 hours starting between 8:00 – 9:00 a.m. 4
- 5 hours starting between 9:00 a.m. – 2:00 p.m. 3
- 5 hours starting between 2:00 – 5:00 p.m. 2
- 5 hours starting between 5:00 p.m. – 4:00 a.m. 1

18. At *approximately* what time of day do you usually feel your best?

- 5:00 a.m. – 8:00 a.m. 5
- 8:00 a.m. – 10:00 a.m. 4
- 10:00 a.m. – 5:00 p.m. 3
- 5:00 p.m. – 10:00 p.m. 2
- 10:00 p.m. – 5:00 a.m. 1

19. One hears about “morning types” and “evening types.” Which one of these types do you consider yourself to be?

- Definitely a morning type 6
- Rather more a morning type than an evening type 4
- Rather more an evening type than a morning type 2
- Definitely an evening type 0

Total: _____

Table - Flow Chart

	00	RZ	D1	D2	D3	D4	D5	D6	D7	W2	W3	W4	W5	W6	M1	M2	M3	M4	M5	M6
Clinician-Rated Measures																				
- SCID	X																			
- HIGH-C	X	X							X	X	X	X	X	X	X	X	X	X	X	X
- SIGH-ADS	X	X							X	X	X	X	X	X	X	X	X	X	X	X
- CGI	X	X							X	X	X	X	X	X	X	X	X	X	X	X
- m-HIGH-C		X	X	X	X	X	X	X	X											
- m-SIGH-ADS		X	X	X	X	X	X	X	X											
- m-CGI		X	X	X	X	X	X	X	X											
- MMSE*	X																			
Independent Evaluator																				
- SIGH-ADS		X							X					X						
- CGI		X							X					X						
- IE Treatment Guess		X							X					X						
Patient-Rated Measures																				
- QIDS	X	X							X	X	X	X	X	X	X	X	X	X	X	X
- Expectation Form	X																			
- PGI	X	X							X	X	X	X	X	X	X	X	X	X	X	X
- MEQ	X	X												X						X
- SCL-90	X	X							X					X			X			X
- sleep log	X	X	X	X	X	X	X	X	X	X	X	X	X	X	X	X	X	X	X	X
- m-QIDS		X	X	X	X	X	X	X	X											
- m-PGI		X	X	X	X	X	X	X	X											
Laboratory and other																				

- PE	X																		
- labs	X																		
- saliva for melatonin		X						X											
- urine for pregnancy**	X						X												

* used only for those aged 60 and above

